
INTRODUCTION AND BACKGROUND
 
Hyperinsulinemic Hypoglycemia (HH) is a rare but growing disease state characterized by frequent episodes of severe symptomatic hyperinsulinemic hypoglycemia, with glucose concentrations low enough (<54 mg/dL) to cause seizures, altered mental status, loss of consciousness, cognitive dysfunction, disability, and possibly death. The predominant form of HH is post-bariatric hypoglycemia (PBH), which occurs in some 29-39% of patients undergoing Roux-en-Y gastric bypass (RYGB) and 10-23% of those undergoing vertical sleeve gastrectomy (VSG) (1-4). HH can also occur as a complication of other upper-gastrointestinal procedures, including esophagectomy (5), gastrectomy (6), and Nissen fundoplication (7). Currently, there are no effective medical therapies for patients with HH.
 
The mechanisms mediating PBH and other forms of HH that occur after gastrointestinal procedures have long been debated, though excessive postprandial secretion of the incretin gut hormone, glucagon-like peptide-1 (GLP-1), has been shown to play a critical role in mediating hyperinsulinism (5-6,8-10). Avexitide is a specific, competitive antagonist of the GLP-1 receptor formed by the terminal deletion of the 8 N-terminus amino acids from exenatide (commercial name Byetta), a GLP-1 agonist. Prior studies conducted by our laboratory and others involving either intravenous (7, 11-13) or subcutaneous (14-16) administration of avexitide have shown normalization of postprandial insulin concentrations with reduction in the occurrence and severity of hypoglycemia and associated symptoms.
 
The most recent study in which our laboratory participated, the PREVENT study (16), was a Phase 2, randomized, placebo-controlled crossover study evaluating two dosing regimens of avexitide (30 mg BID and 60 mg QD) in 18 patients with diet-refractory PBH. In this study, 18 participants received placebo injections for 14 days followed by avexitide 30 mg BID and avexitide 60 mg QD, each for 14 days in random order. The primary outcome was glucose nadir during mixed meal tolerance testing (MMTT) at the end of each 14-day treatment period. In addition, hypoglycemic events captured by SMBG, eDiary, and blinded continuous glucose monitoring (CGM) were captured. The primary and secondary endpoints were met by both avexitide regimens. Compared to placebo, avexitide 30 mg BID and 60 mg QD raised the plasma glucose nadir by 21% (<math>p=0.001</math>) and 26% (<math>p=0.0002</math>) and lowered the insulin peak by 23% (<math>p=0.029</math>) and 21% (<math>p=0.042</math>), corresponding to 50% and 75% fewer participants requiring rescue, respectively. Significant reductions in outpatient rates of Levels 1-3 hypoglycemia were observed, defined, respectively, as SMBG<70 mg/dL, SMBG<54 mg/dL, and a severe event characterized by altered mental and/or physical function requiring assistance. Blinded CGM demonstrated reductions in hypoglycemia without induction of clinically relevant hyperglycemia. Avexitide was well-tolerated, with no increase in adverse events.
		

Based on the safety and tolerability profile of avexitide and the dose-response relationship observed with higher daytime avexitide exposure in the PREVENT trial, we seek to evaluate whether higher dosing regimens of avexitide may confer greater yet protection against hypoglycemia. In addition, given that GLP-1 excursions are also known to occur in forms of HH other than PBH, we seek to evaluate for the first time whether subcutaneous injection of avexitide may provide protection against hypoglycemia in this expanded cohort of patients with HH. Thus, we seek to extend upon the the previously conducted studies by investigating the safety, tolerability and efficacy of avexitide administered as 45 mg BID and 90 mg QD dosing regimens in patients with HH occurring after RYGB, VSG, esophagectomy, gastrectomy, and Nissen fundoplication.

## OBJECTIVES

### *Primary Efficacy Objective*

Evaluate the effect of avexitide injection on the number of diurnal Level 2 hypoglycemia events (ADA, <54 mg/dL) as measured by CGM in patients with severe HH

### *Secondary Efficacy Objectives*

Evaluate the effect of avexitide injection on the:

- Rate of Level 2 hypoglycemia (ADA, <54 mg/dL) as measured by SMBG
- Rate of Level 3 hypoglycemia (ADA, severe hypoglycemia)
- Percent diurnal time <54 mg/dL as measured by CGM
- Postprandial glycemia during standardized mixed meal consumption

### *Exploratory Efficacy Objectives*

Evaluate the effect of avexitide injection on:

- Quality of life (QoL)
- Rate of Level 1 hypoglycemia (ADA, <70 mg/dL) as measured by SMBG in patients with severe HH
- Percent time >250 mg/dL as measured by CGM
- Percent nocturnal time <54 mg/dL as measured by CGM
- Number of nocturnal Level 2 hypoglycemia events (ADA, <54 mg/dL) as measured by CGM
- Characterize the Pharmacokinetic/Pharmacodynamic (PK/PD) profile of avexitide 45 mg BID and 90 mg QD
- Evaluate development of anti-drug antibodies (ADA)

### *Primary Safety Objective*

- Evaluate the safety and tolerability of avexitide

## INVESTIGATIONAL PLAN

### Study Design

**Overview**—This is a Phase 2b, single center, open-label, cross-over study of avexitide injection in patients with surgically-induced severe, diet-refractory HH. Eligible participants must have a confirmed diagnosis of surgically-induced HH and demonstrate severe, diet refractory HH, as documented by presence of at least two severe hypoglycemia events from which at least one must be characterized by glucose <54 mg/dL as measured by CGM during the 14-day Run-in Period while adhering to medical nutritional therapy.

[figure not shown]
Eligible HH indications include hypoglycemia occurring after:

- Bariatric Surgery:
  - Roux-en-Y Gastric Bypass (RYGB) or Vertical Sleeve Gastrectomy (VSG)
- Upper-Gastrointestinal Surgery:
  - Gastrectomy, Esophagectomy, or Nissen Fundoplication

Provisionally eligible subjects will undergo a 14-day Run-In consisting of standard of care (SOC) treatment (medical nutrition therapy) with standardized mixed meal consumption and screening labs and collection of blood to test for anti-drug antibody (ADA) at the end of the 14-day SOC Run-In to confirm eligibility and establish a baseline within 90 days of randomization. Enrolled participants will be randomized to one of two 14-day avexitide dosing regimen orders (Figure 1). Doses are to be self-administered in the outpatient setting via subcutaneous (SC) injection. Throughout the study duration participants will continue to maintain SOC treatment following standard dietary guidelines for management of PBH and will be evaluated by blinded CGM, patient electronic diary (eDiary) and SMBG. At the end of Treatment Periods 1 and 2, participants will repeat baseline assessments with ADA and trough PK samples additionally drawn. At the end of Treatment Period 2, participants will return used and unused study drug vials during the safety follow-up visit.

**Study Duration**— Depending on when a patient completes the Run-In Period, the maximum anticipated time an individual patient will participate in the study will be ~120 days.

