## **STUDY POPULATION**

### **Inclusion Criteria**

Patients must meet all of the following inclusion criteria before study entry to be eligible for enrollment.

1. Able to understand the purpose and risks of the study; willing and able to adhere to scheduled visits, treatment plans, laboratory tests, procedures, and provide written informed consent
2. History of qualifying bariatric or upper-gastrointestinal surgery (RYGB, VSG, gastrectomy, esophagectomy, or Nissen fundoplication) at least 12 months prior to the start of Screening
3. Male or female, at least 18 years old (inclusive) at Visit 1 (Screening)
4. Body mass index (BMI) of up to 40 kg/m^2
5. Has stable body weight, i.e., not varying by >5% for at least 4 months prior to Visit 1 (Screening), as documented by the investigator
6. History of recurrent hypoglycemia refractory to bariatric dietary recommendations occurring after bariatric or upper-GI surgery, as documented in the medical record.
7. At least two severe hypoglycemia events from which at least one must be characterized by glucose <54 mg/dL as measured by CGM during the 14-day Run-in Period while adhering to medical nutritional therapy.
8. If female, must meet the following criteria:
  - a. Not breastfeeding or lactating
  - b. Negative urine pregnancy test result at Visit 4 (Screening) (not applicable to hysterectomized females); urine pregnancy test at Screening must be confirmed negative prior to randomization and dosing.
  - c. If of childbearing potential (including peri-menopausal women who have had a menstrual period within 1 year) must agree to use appropriate birth control (defined as a method which results in a low failure rate, i.e., less than 1% per year, when used consistently and correctly, such as implants, injectables, hormonal contraceptives, some intrauterine

contraceptive devices, sexual abstinence, tubal ligation or occlusion, or a vasectomized partner) during the entire duration of the study. Subjects must practice appropriate birth control as stated above for 4 weeks after the last dose of study drug.

- Nonchildbearing potential is defined as surgically sterile (documented hysterectomy, tubal ligation, or bilateral salpingo oophorectomy) or postmenopausal (defined as 12 months of spontaneous amenorrhea).
- 9. Has no clinically significant abnormal complete metabolic panel (CMP) as judged by the investigator. Note: CMP collected at Visit 4 unless assessed within 6 months prior to randomization.

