## Study Schedule

The screening period comprises:

- Visit 1 (Zoom): Informed Consent, review of medical history, hypoglycemia questionnaire, concomitant medications, assessment of preliminary eligibility
- Visit 2 (Zoom): training on patient eDiary, glucometer use, and Dexcom G6PRO application and activation. Participants begin 14-day Run-In Period
- Visit 3 (Zoom): Check in with patient.
- On day 10 of the Run-In Period, participants place a new Dexcom G6PRO sensor.
- Visit 4 (SHC): On day 14 of the Run-In Period, participants go to SHC for a urine pregnancy test, an ADA draw, and CMP as applicable then consume a standardized liquid mixed meal over 10 minutes, with fingerstick glucose checks every 30 minutes for a total of 180 minutes. Eligible participants are then enrolled, randomized and dispensed study drug.

Enrolled participants will be randomized 1:1 to one of 2 avexitide dosing regimen orders, and will be trained on study medication injection procedures. Avexitide should be injected subcutaneously either once daily in the morning, or twice daily; once in the morning and the second daily dose approximately 12 hours later. During once daily administration (avexitide 90 mg QD), morning dosing will occur at least 60 minutes prior to the first morning meal. During twice daily administration (avexitide 45 mg BID) morning dosing will not be relative to the timing of the first meal of the day. Throughout, patients will follow currently accepted dietary guidelines for treatment of PBH.

- Visit 5 (Zoom): Participants are trained on study drug injection; initiate Treatment Period 1. Place new Dexcom G6PRO device.
- Day 10 of Treatment Period 1: Participants place a new Dexcom G6PRO device.
- Visit 6 (SHC): On day 14 of Treatment Period 1 participants have a PK and an ADA draw, have their final Treatment Period 1 study drug injection and 90 minutes later consume a standardized mixed meal over 10 minutes, with fingerstick glucose checks every 30 minutes for 180 minutes. Participants are dispensed new study drug and initiate a 2-day washout period.
- Day 4 of Treatment Period 2: Participants place a new Dexcom G6PRO device.

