## APPENDIX A

## SCHEDULE OF EVENTS

	DAY-0	RUN-IN PERIOD (DAY-1)	RUN-IN PERIOD (DAY-4)	RUN-IN PERIOD (DAY-10)	RUN-IN PERIOD (DAY-14)	TREATMENT PERIOD 1 (DAY-1)	TREATMENT PERIOD 1 (DAY-10)	TREATMENT PERIOD 1 (DAY-14)	TREATMENT PERIOD 2 (DAY-1)	TREATMENT PERIOD 2 (DAY-4)	TREATMENT PERIOD 2 (DAY-14)
	ZOOM VISIT 1	ZOOM VISIT 2	ZOOM VISIT 3	NO VISIT	STANFORD VISIT 4	ZOOM VISIT 5	NO VISIT	STANFORD VISIT 6	NO VISIT	NO VISIT	STANFORD VISIT 7
Informed Consent	X										
Medical History	X										
Hypoglycemia Questionnaire	X										
Quality of Life Assessments**					X			X*			X*
Physical Exam	X				X*						X*
Preliminary Eligibility Determination	X										
eDiary Training		X									
Glucose Meter Training		X									
Check-In with Patients			X								
Review Dietary Guidelines and SOC Adherence	X	X	X		X	X*		X*			X*
Initiate eDiary and glucometer Use		X									
CGM Training		X									
CGM Placement/Activation		X		X		X*	X*			X*	
Mixed Meal Tolerance Test					X			X*			X*
CGM Removal				X			X*			X*	X*

Trough PK Draw								X*				X*
Blood Draw (CMP)***					X							X*
ADA Draw					X			X*				X*
Urine Pregnancy Test as applicable					X							
Final Eligibility Determination					X							
Randomization					X*							
Dispensing of Study Drug					X*							
Study Drug Injection Training						X*						
14-Day Treatment Period 1 Starts						X*						
2-Day Washout Period Starts								X*				
14-Day Treatment Period 2 Starts									X*			
Concomitant Medications	X	X	X		X	X*		X*				X*
Adverse Events			X		X	X*		X*				X*
Return of Used and Unused Study Drug Vials												X*
Study Drug Accountability												X*

\* Procedures and activities are only applicable to enrolled participants (determined on Visit 4 at Stanford Health Clinic).

\*\* QoL assessments **are not** completed during the visit.

\*\*\* CMP drawn at Visit 4 unless assessed within the prior 6 months.

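### No chemistry panel is scheduled after the first regimen, and the baseline panel may be up to 6 months old, although the overview lists labs at baseline and repeats baseline assessments after both periods

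*Combined protocol and SAP*

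**What the plan says.** The Study Design overview places "standardized mixed meal consumption and screening labs and collection of blood to test for anti-drug antibody (ADA) at the end of the 14-day SOC Run-In", and gives the purpose as "to confirm eligibility and establish a baseline within 90 days of randomization". Later in the same paragraph it says: "At the end of Treatment Periods 1 and 2, participants will repeat baseline assessments with ADA and trough PK samples additionally drawn".

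The operational parts of the document differ:

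- **Appendix A, Schedule of Events.** The row beginning "Blood Draw (CMP" is marked at Visit 4 and Visit 7 only. Its footnote reads "CMP drawn at Visit 4 unless assessed within the prior 6 months".
- **Inclusion Criteria, no. 9.** The same waiver appears: "CMP collected at Visit 4 unless assessed within 6 months prior to randomization".
- **Study Schedule, Visit 6.** The blood draws listed are PK and anti-drug antibody: "On day 14 of Treatment Period 1 participants have a PK and an ADA draw". No CMP is mentioned.
- **Study Schedule, Visit 7.** The text again lists only PK and anti-drug antibody draws, although Appendix A marks a CMP at that visit.

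The Primary Safety Objective is the safety and tolerability of avexitide. The Safety Endpoints section names adverse events and no laboratory endpoint.

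**The concern.** Each participant takes both regimens, one after the other, with a 2-day washout between them. The only chemistry scheduled after dosing starts is at Visit 7, when both regimens have been taken. An abnormal value there could have arisen under either regimen. A change without symptoms that arose in Period 1 would go unseen until the end of Period 2, and would be missed altogether if it had resolved by then.

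The waiver adds a second problem. If the pre-dose value is an old one, a difference at Visit 7 mixes change during treatment with whatever happened in the months before enrolment.

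This matters because safety is a stated primary objective, and because both regimens give 90 mg per day against 60 mg per day in PREVENT. Scheduling a CMP at Visit 7 also shows that the sponsor wants chemistry after dosing.

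**Working it through.** The plan states no figure to reproduce here. The check is a comparison of sections, followed by simple counts.

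**1. Is the Visit 6 gap real, or damage to the table?** Counting columns after the row label, the CMP marks fall in column 5 and in the last column. The trough PK marks fall in column 8 and the last column, and the anti-drug antibody marks in columns 5, 8 and last. PK and antibody samples are drawn at Visit 6 according to the visit text, so column 8 is Visit 6. The CMP row is empty there, so the gap is in the schedule itself.

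**2. Are labs part of baseline?** The overview lists the mixed meal, screening labs and antibody sample together as what confirms eligibility and sets the baseline. On its plain reading, repeating baseline assessments after both periods includes the labs.

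**3. Age of the comparison panel at Visit 7.** Inputs: Period 1 is 14 days, washout 2 days, Period 2 14 days. Six months is taken as about 183 days, and dosing is assumed to start at randomization.

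- Panel drawn at Visit 4: 14 + 2 + 14 = 30 days.
- Panel waived, oldest allowed: 183 + 30 = 213 days, of which 30/213 = 14% falls in the treatment phase.

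The protocol's maximum participation of about 120 days agrees with this: 90 days before randomization + 30 = 120. Any delay between randomization and first dose lengthens both figures equally.

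**4. Panels available, with 20 completers.**

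| | As scheduled | With CMP at Visits 4 (all) and 6 |
|---|---|---|
| Pre-dose panel at Visit 4 | 0 to 20 | 20 |
| After the first regimen alone | 0 | 20 (about 10 per regimen) |
| End-of-regimen panels, total | 20 (about 10 per regimen, all Period 2) | 40 (20 per regimen, paired within participant) |

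**5. Illustration of what the extra panels add.** Suppose an abnormality is present at the end of a given regimen with probability p (an assumption; the documents give no rate). The chance of seeing it at least once in n panels is 1 − (1 − p)^n.

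| p | n = 10 | n = 20 |
|---|---|---|
| 5% | 40% | 64% |
| 10% | 65% | 88% |
| 15% | 80% | 96% |

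These are chances of detection only. As scheduled, all the n = 10 panels follow exposure to both regimens, so an abnormality that is seen still could not be assigned to one of them.

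**6. Extra panels.** Visit 6 adds up to 20. Visit 4 adds as many as would have been waived, 0 to 20. The total is at most 20 + 20 = 40.

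**The case against.** **The overview may not promise a CMP at Visit 6.** It describes antibody samples as additional to the repeated baseline assessments, although the antibody sample is itself in the baseline list. The phrase could therefore mean the non-blood assessments. Appendix A is compatible with that: the meal test and quality of life are marked at Visits 4, 6 and 7, and the physical exam, like the CMP, is not marked at Visit 6. This ambiguity stands. It is a reason to reconcile the sections, and it leaves the absence of chemistry after Period 1 unchanged.

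**The visit text is not exhaustive.** It also leaves out quality of life, adverse events and concomitant medications at Visits 6 and 7. So its silence on the CMP at Visit 6 adds little to Appendix A, and its silence at Visit 7 is a minor drafting point.

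**No laboratory endpoint is compromised.** Adverse events are the only named safety endpoint and are recorded at Visits 3 to 7, so they can be assigned to a period. The objective concerns avexitide overall, and both regimens give the same daily total. This is fair and limits the weight of the point. It does not help with laboratory changes that cause no symptoms.

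**Stronger readings that the documents do not support.**

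- A reader might infer that laboratory changes cannot be tied to the drug in anyone. The 6-month rule is a waiver, so a participant sampled at Visit 4 has a pre-dose value about 30 days before Visit 7.
- A reader might infer a plain conflict between "establish a baseline within 90 days of randomization" and the 6-month waiver. Screening Procedures uses 90 days as the window for preliminary eligibility assessments, and criterion 9 is an eligibility test with its own window. The narrower tension is that the overview places screening labs at the end of the Run-In, while the waiver lets them come from elsewhere.
- A reader might infer that 90 mg per day exceeds every daily dose studied before. The documents give doses for PREVENT only.

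**Conclusion.** The point holds in a limited form. As scheduled, 0 of up to 20 participants have chemistry after the first regimen alone, so a laboratory change at Visit 7 cannot be reliably attributed to a regimen. For participants whose Visit 4 CMP is waived, the comparison value can be about 213 days old instead of about 30, and the change also cannot be reliably separated from change before the study.

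This rests on 6 months being about 183 days, on dosing starting at randomization, and on the plain reading of the overview. The number waived is unknown and could be anywhere from 0 to 20; if it is 0, only the regimen part of the point remains.

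Adding panels would not settle causation. The study is open-label without a concurrent placebo, and a Period 2 panel still follows both regimens. The gain is a recent pre-dose value for everyone and one value after each period, which makes this a cheap improvement and not a flaw that undermines the trial.

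**What to change.** Reconcile the Study Design overview, Inclusion Criteria no. 9, the Visit 6 and Visit 7 text in Study Schedule, and Appendix A, as follows:

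1. In Appendix A, mark the CMP at Visit 4 for every participant. A panel from the previous 6 months may still serve eligibility under criterion 9, but the Visit 4 sample is the safety baseline.
2. Mark the CMP at Visit 6, using the blood draw already scheduled for PK and anti-drug antibodies.
3. List the CMP in the Visit 6 and Visit 7 text, and state in the overview which assessments are repeated.
4. Under Safety Endpoints, add a descriptive table of change from Visit 4 to Visits 6 and 7, by regimen and period.

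Cost: at most about 40 extra panels, one extra table and the text edits. Blood is already drawn at both visits, so no new visit or needle stick is needed. No rule for acting on the Visit 6 result is proposed here; that is a clinical matter for the sponsor and investigator.

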**Figure 1 Diagram of Study Design**

## **Number of Participants**

Up to 20 participants will be enrolled in a 1:1 ratio to each of the two dosing regimen orders shown in Figure 1. Of the enrolled population, at least 50% will be post-RYGB; the remainder will be post-VSG, -gastrectomy, -esophagectomy, or -Nissen fundoplication. Randomization will be stratified by type of surgery RYGB vs Others (including VSG, gastrectomy, esophagectomy, or Nissen fundoplication).

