### **Drug Accountability**

Drug accountability will be maintained by the principal investigator, who will ensure that a current record of investigational product disposition is maintained and that the investigational product is used only in accordance with the approved protocol.

Patients will be instructed to return all used and unused vials of study drug when they come to the clinic for the final study visit. Adherence with the prescribed regimen for each study drug will be estimated by counting the number of used and unused vials.

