- Visit 7 (SHC): On day 14 of Treatment Period 2 participants have a PK and an ADA draw, have their final Treatment Period 2 study drug injection and 90 minutes later participants consume a standardized mixed meal over 10 minutes, with fingerstick glucose checks every 30 minutes for a total of 180 minutes. Participants then remove their Dexcom sensor/transmitter and return their used/unused study drug vials.

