## **Study Procedures**

### **eDiary and Glucometer**

Patients will be trained on the use of an eDiary on Visit 2 in which they will record all hypoglycemia signs, symptoms, and outcomes, any corrective actions taken for hypoglycemia, any assistance received related to an episode, and dietary intake. Patients will also receive a glucometer prior to Visit 2 and be instructed to check fingerstick glucose concentrations whenever they experience hypoglycemic symptoms. Patients will also enter into the eDiary all SMBG glucose values obtained during consumption of the 3 standardized liquid meals. Study personnel will train participants on the use of the eDiary and glucometer.

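### The visit labelled as safety follow-up is Visit 7, the day of the last injection, and no adverse-event contact is scheduled after that day

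*Combined protocol and SAP*

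**What the plan says.** Four places in the combined protocol and SAP bear on which visit this is.

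- Study Design, Overview: at the end of Treatment Period 2, "participants will return used and unused study drug vials during the safety follow-up visit".
- Drug Accountability: patients are told to "return all used and unused vials of study drug when they come to the clinic for the final study visit".
- Study Schedule, Visit 7 (Day 14 of Treatment Period 2): participants "have their final Treatment Period 2 study drug injection and 90 minutes later participants consume a standardized mixed meal", with 180 minutes of fingerstick checks. The entry closes with "Participants then remove their Dexcom sensor/transmitter and return their used/unused study drug vials".
- Appendix A, Schedule of Events: the row "Return of Used and Unused Study Drug Vials" has a single mark, in the last column.

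On safety collection, Appendix A marks adverse events at Visits 3, 4, 5, 6 and 7. At Visit 7 it also marks a physical exam, a metabolic panel and an anti-drug antibody draw. The Safety Endpoints section is a single line on evaluating adverse events and gives no collection window. The eDiary and Glucometer section describes a diary in which "they will record all hypoglycemia signs, symptoms, and outcomes", together with corrective actions, assistance received, diet and meal-test glucose values. General adverse events are not among its stated contents.

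**The concern.** A reader of the overview could expect a safety check after dosing has ended. The detailed schedule shows that the visit carrying that name is the one at which the last dose is given. Nothing is scheduled later.

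Safety and tolerability is the primary safety objective. The total daily dose here is 90 mg, while the earlier PREVENT trial gave 60 mg a day (30 mg BID or 60 mg QD). PREVENT's report of no increase in adverse events therefore does not directly cover the present dose. The Introduction also says that subcutaneous avexitide is being evaluated for the first time in forms of the disease other than the post-bariatric one. An event that first appears after the final dosing day, such as a delayed local or allergic reaction (my examples; the documents name none), would be recorded only if the participant volunteered it. The available text neither describes nor rules out such reporting.

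**Working it through.** **1. Which visit is it?** Vial return is scheduled once. The overview attaches it to the safety follow-up, Drug Accountability to the final study visit, and the Study Schedule and Appendix A to Visit 7. These can only be the same visit. In the text available for review, the lower half of the Appendix A table has one more column than its header. This is not a hidden later visit: the trough PK and antibody marks in that last column match the draws that the Study Schedule lists at Visit 7.

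**2. Does the stated duration leave room for a later contact?** Inputs: up to 90 days of screening and Run-In before randomization (Study Design; Screening Procedures), two 14-day treatment periods (Study Design), and a washout (Study Schedule, Visit 6: "Participants are dispensed new study drug and initiate a 2-day washout period").

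90 + 14 + 2 + 14 = 120 days

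This reproduces the plan's stated maximum of about 120 days and leaves about 0 days after the last dose.

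**3. Scheduled time on site after the last injection.** Inputs from the Visit 7 entry: 90 minutes to the meal, a 10-minute meal, 180 minutes of checks.

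- Checks timed from the start of the meal: 90 + 180 = 270 minutes = 4.5 hours.
- Checks timed from the end of the meal: 90 + 10 + 180 = 280 minutes, about 4.7 hours.

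Sensor removal and vial return follow, so this is roughly a minimum. The adverse-event query at Visit 7 has no stated clock time and could come before or after the injection.

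**4. What the adverse-event marks can cover.**

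| Visit | Timing | Can it review time on drug? |
|---|---|---|
| 3, 4 | Run-In | No |
| 5 | Day 1 of Treatment Period 1 | Only if the query follows the first dose |
| 6 | Day 14 of Treatment Period 1 | Yes |
| 7 | Day 14 of Treatment Period 2 | Yes |
| Any later contact | None scheduled | Not applicable |

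Of 5 marks, 2 or possibly 3 can review time on drug. None falls after the last dosing day.

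**5. The two regimens in sequence.** Events that start after the first regimen's last dose still get a scheduled query at Visit 7, 2 + 14 = 16 days after Visit 6. Events that start after the second regimen's last dosing day get none.

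**6. How many people.** "Up to 20 participants will be enrolled in a 1:1 ratio to each of the two dosing regimen orders", so at most 20 participants are affected, with up to about 20 / 2 = 10 finishing on each regimen.

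**The case against.** The strongest reply is that little is left uncovered. Both regimens give the same drug at the same 90 mg a day. From the start of Treatment Period 1 to Visit 7 is 14 + 2 + 14 = 30 days and includes a 2-day break from drug. Delayed reactions to most doses would surface in that time and could be picked up at Visit 6 or Visit 7. The overview also places its visit at the end of Treatment Period 2 and does not expressly promise a later, off-drug visit, so part of the problem is the label. Figures 1 and 2 could not be seen, and the consent and contact pages are not in the reviewed text; instructions for reporting later events could be there.

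Most of this stands, and it limits the point to events that begin after the final dosing day. It does not remove the point, because for those events the visible plan schedules no capture at all.

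A reader might infer more than the documents support:

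- *That observation after the last dose is capped at 4.5 hours.* No cap is stated, and the closing steps come after the timed checks.
- *That only Visits 6 and 7 can review time on drug.* Visit 5 falls on the first dosing day and may do so too.
- *That the comparison of 45 mg BID with 90 mg QD is biased.* Order is randomized 1:1, so the uncovered time falls after each regimen in about equal numbers.
- *That efficacy is affected.* The efficacy endpoints are defined within the treatment periods or from the standardized meals, all complete by the end of Visit 7.

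**Conclusion.** The point holds as a gap in safety capture. The visit called safety follow-up is Visit 7, a dosing day, and events that start after that day have no scheduled capture in any of up to 20 participants. The number of events missed cannot be estimated, because the documents give neither a half-life nor a rate of late-onset events; they may go unrecorded, and nothing stronger can be said. The conclusion assumes that the figures and removed pages contain no later contact; nothing in the available text points to one, and the 120-day sum leaves no time for it. The change is worth making because safety is a stated objective at a daily dose above the earlier trial's and the remedy is cheap.

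**What to change.** Add one remote adverse-event contact after the last dose, by telephone or by Zoom as at Visits 1 to 3 and 5, to the Study Design overview, the Study Schedule and Appendix A. About 7 days is a reasonable example. It should in any case be no sooner than 2 days, the length of the plan's own washout; that is a floor taken from the schedule and has no pharmacokinetic basis in the documents. State under Safety Endpoints that adverse-event collection runs to that contact, and call Visit 7 the end-of-treatment visit.

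The cost is a schedule amendment and one call for each of at most 20 participants, with no added clinic visit, sample or sensor. Maximum participation becomes 120 + 2 = 122 days with a 2-day contact, or 120 + 7 = 127 days with a 7-day contact; restate the stated maximum if the longer interval is used. Matching the 4-week contraception period in the inclusion criteria would give 120 + 28 = 148 days, which is more than this point requires. Events starting after the chosen contact would still be missed. A 2-day contact fits delayed reactions poorly, which is the reason to prefer the longer interval.
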